3. PARTICIPANT ELIGIBILITY CRITERIA

3.1. Inclusion Criteria

Participants must meet the following criteria upon screening examination to be eligible to participate in the study:

1. Patient has signed the Informed Consent (ICF) prior to any study procedures being performed and is able to comply with protocol requirements.
2. Must be able to swallow ribociclib.

Age Criteria, Life Expectancy and Language Skill

3. Age: ≥ 70 years at time of enrollment
 - ≥ 70 to < 74 years OR ≥ 75 years
 - NOTE: A minimum of 20 participants must be ≥ 75 years. The remaining 20 participants may be ≥ 70 to < 74 years OR ≥ 75 years.
4. Subjects must be able to communicate with the investigator and comply with the requirements of the study procedures.

Nature of Illness and Treatment History

5. Patient has a histologically and/or cytologically confirmed diagnosis of estrogen-receptor positive and/or progesterone receptor positive breast cancer, HER2-negative breast cancer defined as a negative in situ hybridization test or an IHC status of 0, 1+ or 2+, and metastatic breast cancer.
6. First or second line endocrine therapy for metastatic disease. One prior line of chemotherapy for metastatic disease is allowed.

Laboratory Information

7. Patient has adequate bone marrow and organ function as defined by the following laboratory values at screening:
 - a. Absolute neutrophil count $\geq 1.5 \times 10^9$ /L
 - b. Platelets $\geq 100 \times 10^9$ /L
 - c. Hemoglobin ≥ 9.0 g/dL
 - d. Patient must have the following laboratory values within normal limits or corrected to within normal limits with supplement before the first dose of study medication:
 - Sodium
 - Potassium
 - Magnesium
 - Total Calcium (corrected for serum albumin)
 - Phosphorous
 - e. Serum creatinine < 1.5 mg/dL or creatinine clearance ≥ 50 mL/min
 - f. In the absence of liver metastases, alanine aminotransferase (ALT) and aspartate aminotransferase (AST) $< 2.5 \times$ ULN. If the patient has liver metastases, ALT and AST $< 5 \times$ ULN
 - g. Total bilirubin $<$ ULN; or total bilirubin $\leq 3.0 \times$ ULN or direct bilirubin $\leq 1.5 \times$ ULN in patients with well-documented Gilbert's Syndrome.

Cardiac Information

8. Patient with available standard 12-lead ECG with the following parameters at screening (defined as the mean of the triplicate ECGs):
 - a. QTcF interval at screening <450msec (using Fridericia's correction)
 - b. Resting heart rate 50-90bpm

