This study will be an open label, single arm, Phase IIA safety and tolerability study to describe the toxicity profile of ribociclib in combination with an aromatase inhibitor in patients age 70 and older with hormone receptor positive metastatic breast cancer. We plan to study 40 evaluable subjects, stratifying on age such that at least 20 evaluable participants are aged 75 years or older. There will be one interim analysis after 20 evaluable participants have completed one cycle of the drug.

All patients who begin study treatment will be included in the analysis of all clinical endpoints.

Objectives:**Primary objective:**

To estimate the safety and tolerability of ribociclib in combination with an aromatase inhibitor in adults aged 70 or older with hormone receptor positive metastatic breast cancer.

Secondary objectives:

1. To describe the full toxicity profile including all grades
2. To estimate the rate of worst grades of myelosuppression (neutropenia, leukopenia, thrombocytopenia, and anemia), neutropenic fever, GI side effects (nausea, diarrhea, decreased appetite, vomiting, stomatitis), fatigue, neuropathy, and thromboembolism
3. To describe rates of dose reductions, dose holds, and hospitalizations
4. To estimate objective response rate and clinical benefit rate as defined by modified RECIST (1.1) criteria
5. To estimate median progression-free and overall survival

6. To determine average plasma steady-state ribociclib C_{trough} concentrations in patients over the age of 70 years

Exploratory objectives:

1. To estimate the rate of adherence to ribociclib
2. To explore factors other than chronologic age that can affect toxicity rates as identified using a cancer-specific geriatric assessment
3. To describe the results of the Was It Worth It (WIWI) and Overall Treatment Utility (OTU) Questionnaires

Endpoints:**Primary:**

The primary endpoint is the incidence of grade 2 and above toxicities attributed to ribociclib.

Secondary:

1. All toxicities associated with the combinations as measured by NCI CTCAE v.4.03
2. Dose reductions
3. Dose holds
4. Hospitalizations
5. Response as determined by RECIST (1.1) criteria
6. Progression free survival defined as the time from start of treatment to the first of the following disease events: local/regional/distant recurrence, invasive contralateral breast disease, second primary or death due to any cause.
7. Overall survival defined as the time from start of treatment to death due to any cause

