1. GOALS AND OBJECTIVES (SCIENTIFIC AIMS)

1.1. Primary Objective

- To estimate the safety and tolerability of the combination of ribociclib and an aromatase inhibitor in adults age 70 or older with hormone receptor positive metastatic breast cancer.

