4.2.2. Slot verification and reservation

Eligible participants are stratified based on age. Designated study staff should call the DCC to verify current slot availability, and to reserve a slot for a specific prospective subject. Slots can only be held for a limited time by an institution.

The DCC should be notified of cancellations of prospective participants holding slots as soon as possible.

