4.2.3. Registration Process

To register a participant, the subsequent procedure is to be followed.

1. The participating site's data manager/coordinator/research nurse should contact the DCC via telephone or email to provide notification regarding the pending registration and communicate desired timeline of the registration, especially if it must be completed promptly to meet the registration window.
2. The data manager/coordinator/research nurse should then e-mail copies to [contact] of the following documents to the DCC:
 - o Registration Cover Sheet ([Appendix C](#))
 - o Completed Eligibility Criteria List (printed from [Section 3.0](#) of the protocol)

- Source documentation to support eligibility criteria**
- Signed informed consent document
- Signed HIPAA authorization form (if separate from the informed consent document)
- Signed subject's Bill of Rights (COH only)

**For COH participants, provide copies of source documentation only if not readily available as a finalized record in the COH Electronic Medical Record (EMR).

3. After having received all transferred documentation, the DCC will complete and review the documents to verify eligibility, working with the participating site as needed to resolve any missing required source elements. A subject failing to meet all protocol eligibility requirements will not be registered.
4. Once eligibility has been confirmed, DCC staff will register the participant by: assigning a subject accession number, register the subject on study centrally into MIDAS for non-COH participants (the COH CRC will directly accession into MIDAS), and enter the subject into the eCRF system, Medidata RAVE.
5. Once registration has been completed, DCC staff will send a Confirmation of Registration Form, including the participant study number to:
 - the site study team: site PI, treating physician, protocol nurse, CRC and pharmacy
 - the COH sponsor team designees

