4.4. Stratification

Participants will be stratified based on age. A minimum of 20 evaluable participants ≥ 75 years must be enrolled. The remaining 20 evaluable participants may be ≥ 70 to < 74 years OR ≥ 75 years.

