13 STATISTICAL CONSIDERATIONS

13.1 Study Design

This study will be an open label, single arm, Phase IIA safety and tolerability study to describe the toxicity profile of ribociclib in combination with an aromatase inhibitor in patients aged 70 and older with hormone receptor positive metastatic breast cancer. We plan to study 40 evaluable participants. Participants that receive one dose of treatment will be considered evaluable, anyone that does not receive treatment will be replaced. We plan to stratify based on age such that at least 20 participants are aged 75 years or older. There will be one interim analysis after 20 participants have completed one cycle of the drug.

13.1.1 Primary Objective:

To estimate the safety and tolerability of the combination of ribociclib and an aromatase inhibitor in adults age 70 or older with hormone receptor positive metastatic breast cancer

13.1.2 Secondary Objectives:

1. To describe the full toxicity profile including all grades
2. To estimate the rate of worst grades of myelosuppression (neutropenia, leukopenia, thrombocytopenia, and anemia), neutropenic fever, GI side effects (nausea, diarrhea, decreased appetite, vomiting, stomatitis), fatigue, neuropathy, and thromboembolism
3. To describe rates of dose reductions, dose holds, and hospitalizations
4. To estimate objective response rate and clinical benefit rate as defined by modified RECIST (1.1) criteria
5. To estimate median progression-free and overall survival
6. To determine average plasma steady-state ribociclib C_{trough} concentrations in patients over the age of 70 years

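### Age bands run from 70 to under 74 and then from 75, so 74-year-olds meet the ≥70 criterion but no band; the response denominator and the two eligibility lists also need reconciling

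*Combined protocol and SAP*

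**What the plan says.** **Age.** Criterion 3 of Section 3.1 sets a floor of 70 years at enrollment. A bullet beneath it gives two bands. A note then requires at least 20 patients aged 75 or over and repeats the bands for the rest: "The remaining 20 participants may be ≥ 70 to < 74 years OR ≥ 75 years". Section 4.4 says the same: "The remaining 20 evaluable participants may be ≥ 70 to < 74 years OR ≥ 75 years".

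Elsewhere there is no gap. The primary objective in Section 1.1 is to estimate safety and tolerability "in adults age 70 or older with hormone receptor positive metastatic breast cancer". The synopsis (Study Design) describes "stratifying on age such that at least 20 evaluable participants are aged 75 years or older", and Section 13.1 states: "We plan to stratify based on age such that at least 20 participants are aged 75 years or older".

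**Registration.** Section 4.2.2 states: "Eligible participants are stratified based on age". Slots are checked and reserved through the data coordinating center. Under Section 4.2.3 the site sends the center a completed eligibility list printed from Section 3.0, the center verifies it, and "A subject failing to meet all protocol eligibility requirements will not be registered".

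**Response population.** The synopsis (Study Design) puts every patient who starts treatment into the analysis of all clinical endpoints. Section 12.1 limits objective response to patients with measurable disease at baseline, at least one cycle of therapy and a re-evaluation; progression before the end of cycle 1 also counts. Section 13.4 plans exact intervals for the objective response rate (ORR) and clinical benefit rate (CBR) but names no denominator.

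**Eligibility lists.** The synopsis has an abbreviated list; Sections 3.1 and 3.2 hold the full one.

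**The concern.** The bands do not cover the population that their own parent criterion defines. Because they are part of the text that decides registration, the wording can act on patients. If it is applied as printed, 74-year-olds are turned away and the estimate covers ages 70 to 73 and 75 upward, not the population in the primary objective.

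The loss might also be hard to see. Section 4.3 asks for a screening log of people who meet the age criteria, so someone refused on age might not be logged under that sentence, although footnote h of the study calendar asks for a broader log.

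The secondary points are of a different kind. Two stated response populations allow two ORRs from the same data, and the choice could be made after the data are seen. Two eligibility lists that disagree allow a patient to be registered under Section 3 without meeting the synopsis.

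**Working it through.** **1. The plan's own precision (Section 13.2).** Inputs: n = 40, exact Clopper-Pearson 95% limits (Section 13.4).
- 20/40 gives 0.338 to 0.662, half-width 0.162. This is the maximum over all possible counts. It agrees with the stated 0.34, 0.66 and 0.16 after rounding.
- P(at least one event at true rate 0.05) = 1 − 0.95^40 = 0.8715, which agrees with 87 in 100.

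Neither figure uses the age bands, so neither changes.

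**2. Which ages are covered.** The bands are 70 ≤ age < 74, or age ≥ 75.

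| Age | Lower band | Upper band |
|---|---|---|
| 70, 73, 73.99 | yes | no |
| 74, 74.5, 74.99 | no | no |
| 75 | no | yes |

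Reading age in completed years does not help, because the lower band then ends at 73. With an upper limit of 75, every age from 70 falls in exactly one band.

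**3. How many patients.** The documents give no age distribution. At most 20 of the 40 can be under 75. Age 74 is one of the five single-year ages from 70 to 74, so an even spread (assumption) gives 1/5 = 20%, and 20% of 20 = 4. An assumed range of 10% to 30% gives 2 to 6.

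**4. Effect on the overall toxicity rate if they are refused and replaced.** Suppose toxicity at 74 differs from that in the replacements by 20 percentage points (assumption).
- 4 replaced: 4/40 × 20 = 2 points.
- 6 replaced: 6/40 × 20 = 3 points.

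Both are small beside a half-width of 16 points.

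**5. ORR under the two stated populations.** All counts are assumed: 12 responders; 8 of 40 patients without measurable disease, none of whom responds; and all of the other 32 meeting the remaining conditions of Section 12.1.
- All treated: 12/40 = 30.0% (exact 95% interval 16.6 to 46.5%).
- Section 12.1: 40 − 8 = 32, and 12/32 = 37.5% (21.1 to 56.3%).

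The choice of denominator moves the estimate by 7.5 points.

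**6. Patients without target lesions.** Section 12.4.2 gives complete response, stable disease and progression criteria for non-target lesions. In Table 12.4.3, however, every row that ends in something other than progression needs a target-lesion status. The overall response of a non-progressing patient with no target lesion is therefore not stated.

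**7. The two eligibility lists.**

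| Item | Synopsis | Section 3 |
|---|---|---|
| Disease measurability | Measurable, or CT/MRI-assessable lytic or mixed bone-only disease | No criterion |
| Life expectancy | More than 6 months | Named in the heading above criterion 3; no criterion follows |
| Untreated brain metastases | Excluded | Some cases listed among the exceptions (3.2, criterion 5) |
| Symptomatic visceral spread | Excluded where it risks life-threatening complications | No such exclusion |
| Residual toxicity exception | Alopecia | Alopecia or peripheral neuropathy (3.2, criterion 14) |

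**The case against.** The best defence on age is that the intention is plain. The parent line says 70 or over, the objective agrees, and the only cut used elsewhere is 75. That stands as evidence of intent. It does not change what is printed three times in the sections that govern registration and stratification.

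Three stronger readings are tempting, and the documents do not support them.
- *Sites would treat 74-year-olds differently on a wide scale.* One center reserves slots and verifies every eligibility packet, so divergence is largely confined to pre-screening before a site contacts the center.
- *An enrolled 74-year-old has no stratum for the by-age tables.* The single cut at 75 in Section 13.1 places that patient below 75, and the quota counts only those aged 75 or over. By-age outputs are also descriptive.
- *Sample size or precision suffers.* Step 1 shows that it does not.

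On response, it can be said that Section 12.1 is the more specific rule, that the synopsis sentence is general and not repeated in Section 13, and that classifying patients under 12.1 covers the components of CBR. These are fair arguments for preferring 12.1, but no text says that it governs, and no denominator is named for CBR. A reader might also infer that early stoppers shrink the 12.1 denominator by a predictable number, for example by applying the 7.5% adverse-event discontinuation rate in Section 2.4.1. That rate covers a whole trial, not the period before the first scheduled scan ahead of cycle 3. Section 5.5 also continues chart review for progression and response after treatment ends without progression, so such patients may still be re-evaluated.

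On eligibility, an abbreviated list may leave criteria out. That does not explain criteria that it adds or states differently.

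**Conclusion.** The age bands are wrong as written. Taken literally at registration, they exclude 74-year-olds and narrow the population below that of the primary objective. On assumed shares, 2 to 6 of at most 20 under-75 places are involved. The resulting shift in the overall toxicity rate is likely to be a few points at most, which rests on the assumed 20-point difference. If 74-year-olds are enrolled, the overall estimate is unaffected. This is an error in an operative threshold, not a flaw in the design or its precision.

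The response denominator is a real but secondary conflict. The 30.0% and 37.5% show its possible size under assumed counts and are not forecasts. The differences between the eligibility lists are also real; this review takes no view on which criterion is right.

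**What to change.** - **Age.** Change the upper limit of the lower band from 74 to 75 in the criterion 3 bullet, the criterion 3 note and Section 4.4. Name the strata in Section 13.4 as under 75 and 75 or over, matching Section 13.1.
- **Response.** In Section 13.4, state one denominator for ORR and one for CBR. Beside Table 12.4.3, say how patients without target lesions are classified, using the criteria already in Section 12.4.2. A sensitivity analysis of ORR on the other stated population is optional.
- **Eligibility.** Reconcile the synopsis with Sections 3.1 and 3.2 on all five items in the table.

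The cost is one number in three places, a few sentences and the alignment of two lists. No patients, visits or data are added.

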Older adults are underrepresented in clinical trials. Despite pronounced changes in drug metabolism, absorption, and distribution with increasing age, limited evidence exists to guide therapy with targeted agents in the older adult population. Evidence now suggests that targeting the CDK/RB pathway has the potential to control ER+ breast cancer progression. To date, clinical data from LEE011 (ribociclib) and PD0332991 (palbociclib) have demonstrated efficacy and tolerable adverse event safety profiles. As the MONALEESA-2 trial demonstrates, the combination of ribociclib and endocrine therapy is a novel targeted treatment approach for postmenopausal women with hormone receptor positive, human epidermal growth factor receptor 2 (HER2)-negative advanced breast cancer. The combination improves progression-free survival compared to endocrine therapy alone. However these studies primarily focused on women less than age 65. For example, the randomized phase II trial (MONALEESA-2) of ribociclib and letrozole compared to letrozole alone (mean age 62) included only 295 patients study wide aged 65 and older and 373 patients aged less than 65 years study-wide with no published cohort data for enrolled patients over the age of 70. The phase III trial (PALOMA-3) of PD0332991 (mean age 57, respectively) included only 25% of participants age 65 and older, while not reporting on participants aged 75 and older (personal communication with [name], 21 August 2015).

The most common adverse events of ribociclib in combination with endocrine therapy are neutropenia, leukopenia, and fatigue. In particular, MONALEESA-2 patients receiving the combination ribociclib and letrozole experienced grade 3 or 4 neutropenia (59.3%), leukopenia (21%), or fatigue (2.4%). In particular, there is a decrease in bone marrow reserve with aging, hence amplifying the potential risk of neutropenia and myelosuppression. Older adults often have other co-morbid medical conditions which may predispose them to thromboembolism thereby increasing the risk. Because of this, a definitive study in the older adult population will diminish any reservations oncologists may have in prescribing ribociclib with an aromatase inhibitor, and can provide guidance regarding the dosing and toxicity management in older adults.

Study Design:

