The relationship between plasma trough and percent drop in neutrophil and platelet counts will be analyzed using linear models methods.

Abbreviated Eligibility Criteria:

Inclusion Criteria

- Hormone receptor positive metastatic breast cancer.
- First or second line endocrine therapy for metastatic disease. One prior line of chemotherapy for metastatic disease is allowed.
- Age: ≥ 70 years and life expectancy > 6 months
- Measurable disease per RECIST (1.1), or bone-only lytic or mixed lytic and blastic lesions that would be accurately assessed by means of computed tomography (CT) or magnetic resonance imaging (MRI).
- The ability to swallow and retain oral medication
- Resolution of all acute toxic effects of prior therapy or surgical procedures to CTCAE Grade ≤ 1 (except alopecia)

Exclusion Criteria

- Untreated brain metastases or symptomatic visceral spread at risk for life-threatening complications
- Concomitant CYP3A strong inhibitors or inducers
- Prior therapy with a CDK inhibitor

Investigational Product Dosage and Administration:

Ribociclib: Administered orally with food on Days 1-21 in each 28-day cycle. Starting dose: 600mg/day.
Aromatase inhibitor: Administered per treating investigator's discretion during each 28-day cycle; dosing should follow the package insert guidelines.

Clinical Observations and Tests to be Performed:

Clinical Observations/ Tests/ Questionnaires: medical history and demographics, physical exams, vital signs, performance status, routine laboratory tests, pill diary assessment, AE assessment, disease assessment, geriatric assessment, Was It Worth It Questionnaire assessment, Overall Treatment Utility assessment. Participants will be followed for survival.

Correlative Biology Studies: From participants who consent to research blood sample collection, a baseline sample of blood will be collected for future studies.

TABLE OF CONTENTS

SECTION	PAGE
Experimental Design Schema	3
Protocol Synopsis.....	4
Table of Contents	8
List of Tables and Figures.....	10
Abbreviations.....	11
1. Goals and Objectives (Scientific Aims).....	12
2. Background	12
2.1. Introduction/Rationale for Development	12
2.2. Rationale for Studying Cancer Therapy in Older Adults.....	12
2.3. Factors Other than Chronological Age that Impact Drug Tolerance	13
2.4. Ribociclib	14
2.5. Overview and Rationale of Study Design	15
3. Participant Eligibility Criteria	17
3.1. Inclusion Criteria	157
3.2. Exclusion Criteria.....	18

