5.7.1. Prohibited until end of protocol therapy

End of protocol therapy is when treatment with ribociclib will no longer continue.

- No other investigational therapy should be given to participants
- No anticancer agents other than the study medications administered as part of this study protocol should be given to participants. If such agents are required for a participant then the participant must first be withdrawn from the study.
- Co-medication that may interfere with study results; e.g. immuno-suppressive agents other than corticosteroids, such as systemic cyclosporine and tacrolimus are prohibited during the treatment phase of the study, unless discussed with principal investigator felt to be of low clinical risk to the participant.
- Use of herbal medications may have unknown interactions with the metabolism of the study agents, and therefore are prohibited from use during the treatment phase of the trial.
- Strong CYP3A inhibitors/inducers including St. John's Wort and Grapefruit. Refer to [Appendix B](#) for an extensive list.
- Drugs known to cause QT interval prolongation. Refer to [Appendix B](#) for an extensive list.
- Hormone replacement therapy, topical estrogens (including any intra-vaginal preparations), megestrol acetate and selective estrogen-receptor modulators (eg, raloxifene).

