Other investigational and antineoplastic therapies	Other investigational therapies must not be used while the patient is on the study. Anticancer therapy (chemotherapy, all SERMS (including raloxifene), biologic or radiation therapy, and surgery) other than the study treatments must not be given to patients while the patient is on the study medication. If such agents are required for a patient then the patient must be discontinued study drug.

¹ NTI = narrow therapeutic index drugs whose exposure-response indicates that increases in their exposure levels by the concomitant use of potent inhibitors may lead to serious safety concerns (e.g., Torsades de Pointes) or drugs which have <2-fold difference in the minimum toxic concentrations and minimum effective concentrations in the blood.

² Herbal product

³ P-gp inducer

⁴ The list provided is as of January 2018. Check <https://www.crediblemeds.org/healthcare-providers/drug-list> for the most updated list.

As far as possible, avoid co-administration of QT prolonging drugs or any other drugs with the potential to increase the risk of drug-related QT prolongation (e.g., via a potential DDI that increases the exposure of ribociclib or the exposure of the QT prolonging drug). A definitive list of drugs with a known risk, possible risk, or conditional risk of QT prolongation and/or Torsades de Pointes (TdP) is available online at qtdrugs.org. Source: Novartis PK Sciences Memorandum: Drug-Drug Interactions (DDI) and Co-medication Considerations for Novartis Clinical Trials (January 2018), which is compiled from Indiana University "Clinically Relevant" Flockhart Table™, University of Washington Drug Interaction Database, and FDA Drug Development and Drug Interactions: Table of Substrates, Inhibitors and Inducers.

List of medications to be used with caution during study drug treatment

Category	Drug Name
Moderate CYP3A4/5 inhibitors	Aprepitant, amprenavir, asafoetida resin (Ferula asafoetida) cimetidine, crizotinib, diltiazem, faldaprevir, imatinib, isavuconazole, netupitant, nilotinib, tofisopam, Schisandra sphenanthera (nan wu wei zi), verapamil
Moderate CYP3A4/5 inducers	Bosentan, dabrafenib, efavirenz, etravirine, genistein, lopinavir ⁵ , modafinil, naftcilin, telotristat

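### Criterion 5 accepts IHC 2+ as HER2-negative without requiring a negative in situ hybridization result

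*Combined protocol and SAP*

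**What the plan says.** Criterion 5 of Section 3.1 asks for hormone receptor positive disease and "HER2-negative breast cancer defined as a negative in situ hybridization test or an IHC status of 0, 1+ or 2+, and metastatic breast cancer". The list is binding: "Participants must meet the following criteria upon screening examination to be eligible to participate in the study". Section 4.2.3 has sites send an eligibility list printed from Section 3.0, with supporting source documents, and adds: "A subject failing to meet all protocol eligibility requirements will not be registered".

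The synopsis, under Abbreviated Eligibility Criteria, gives the disease criterion only as "Hormone receptor positive metastatic breast cancer", with no mention of HER2. The synopsis rationale describes the combination as a treatment for "postmenopausal women with hormone receptor positive, human epidermal growth factor receptor 2 (HER2)-negative advanced breast cancer".

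On other treatment, Section 5.7.1 says "No anticancer agents other than the study medications administered as part of this study protocol should be given to participants", and continues "If such agents are required for a participant then the participant must first be withdrawn from the study". Appendix B repeats the ban and names biologic therapy in it: "Anticancer therapy (chemotherapy, all SERMS (including raloxifene), biologic or radiation therapy, and surgery) other than the study treatments must not be given to patients".

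**The concern.** The criterion accepts a negative ISH result as proof of HER2-negative status, so it treats ISH as informative about HER2. Its second limb then accepts IHC 2+ on its own, even when ISH has been done and is positive. A site applying the text as printed would have to classify that tumour as HER2-negative, and the coordinating center would have no written ground to refuse the registration.

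Two things are at stake. The first is participant protection: a patient outside the intended population would be treated under a rule that excludes other anticancer agents for as long as she stays on protocol therapy. The second is what the efficacy estimates describe. The Study Design paragraph of the synopsis includes everyone who begins treatment in the analysis of all clinical endpoints, so such a patient would not be removed later.

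**Working it through.** The plan gives no figure on this point to reproduce, and the sample-size statements in Section 13.2 do not involve HER2. The check is one of logic, followed by a rough size.

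**1. The rule as written.** Eligible on HER2 if ISH is negative OR IHC is 0, 1+ or 2+. Four IHC results by three ISH states give 12 combinations:

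| IHC | ISH negative | ISH positive | ISH not done |
|---|---|---|---|
| 0 | eligible | eligible | eligible |
| 1+ | eligible | eligible | eligible |
| 2+ | eligible | **eligible** | **eligible** |
| 3+ | eligible | not eligible | not eligible |

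Ten of 12 combinations pass. The only tumours refused are IHC 3+ with ISH positive or not done. The two cells in bold are the gap.

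**2. Does other text close it?**
- Section 3.2: none of the 16 exclusion criteria mentions HER2. Exclusion 10 concerns other concurrent medical conditions, not the receptor status of the study cancer.
- Synopsis: its criteria are looser still, with no HER2 requirement.
- Section 11.0: the calendar's eligibility row refers back to Section 3.0 and adds no rule.
- Section 4.2.3: source documents are sent, but they are judged against the same wording. A report of IHC 2+ with positive ISH would satisfy it.
- The opening of Section 4.2 and Appendix C (the registration coversheet) were not in the text available for review, so the search does not cover them.

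**3. Size.** The documents give no rate, so these inputs are assumptions: 15% to 40% of candidates are IHC 2+, and 5% to 25% of those are ISH positive.
- Low: 0.15 × 0.05 = 0.0075, and 0.0075 × 40 = 0.3 patients.
- High: 0.40 × 0.25 = 0.10, and 0.10 × 40 = 4 patients.

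The high figure multiplies both upper extremes and supposes that no investigator screens such a patient out. The IHC 2+ tumours with no ISH result are not in this count, because the documents give nothing from which to size them.

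**4. Effect on an estimate.** With 40 in the denominator, one patient can move a response proportion by at most 1/40 = 2.5 percentage points, and four by at most 4 × 2.5 = 10 points. For comparison, Section 13.2 gives a 95% half-width of up to 16 points for a proportion at n = 40. Section 12.1 restricts response evaluability to patients with measurable disease, at least one cycle (or earlier progression) and a re-evaluation. On that smaller denominator each patient weighs somewhat more.

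**5. Candidate corrections.** Replacing 'or' with 'and' would pass only IHC 0, 1+ or 2+ with negative ISH (3 of 12). It would shut out IHC 0 and 1+ tumours that had no ISH test. Requiring negative ISH only when IHC is 2+ removes exactly the two bold cells and leaves 8 of 12. Three of those 8 are discordant and still need a stated rule: IHC 0 with positive ISH, IHC 1+ with positive ISH, and IHC 3+ with negative ISH.

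**The case against.** The strongest reply is that this is a drafting slip with little practical effect. Investigators in this field would probably not enrol an IHC 2+, ISH-positive patient. On the low assumptions fewer than one such patient is expected. The primary endpoint, grade 2 or higher toxicity attributed to ribociclib, is not shown to depend on HER2 status. Response, PFS and OS are secondary and descriptive, with no hypothesis test. All of that stands, and it limits the severity. It does not remove the point: an eligibility list that relies on an unwritten correction does not do its job across several sites.

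The documents also do not say that ISH overrides IHC, and criterion 5 itself lists 2+ as negative. That is fair. The argument here needs only the criterion's own use of a negative ISH result as proof of HER2-negative status.

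Three stronger readings are tempting and are not supported:
- A reader might infer that the patient is barred from other cancer treatment altogether. Section 5.7.1 allows other agents once she is withdrawn, and Section 5.4 lets protocol therapy end on investigator judgment or withdrawal of consent. The ban lasts only while she is on protocol therapy.
- A reader might infer that every background figure comes from HER2-negative disease. Section 2.4.1 says all but one patient in each group of the supporting randomized trial was HER2-negative, and Section 2.4.2 does not state HER2 status for the other trials that it cites.
- A reader might infer that HER2 reports are not collected at registration. Section 4.2.3 already requires source documents in support of eligibility, or a finalized record in the sponsor's own medical record system.

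**Conclusion.** The point holds on the wording. Criterion 5 admits IHC 2+ tumours with positive or missing ISH as HER2-negative, no text available for review corrects it, and the registration check inherits it. The criterion therefore does not secure the population on which the rationale rests.

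The expected number is small, probably below one to a few of 40. That range rests wholly on assumed rates, and the documents cannot narrow it. The consequence is mainly one of participant protection. The possible shift in secondary efficacy estimates comes second, and no effect on the primary toxicity endpoint or the sample size is claimed. This should be fixed, but it does not put the trial's main result in doubt.

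**What to change.** Reword criterion 5 so that IHC 2+ counts as HER2-negative only with a negative ISH result. For example: *HER2-negative, meaning IHC 0 or 1+, or a negative ISH test; if IHC is 2+, a negative ISH result is required.* Add a sentence saying how discordant results are classified (IHC 0 or 1+ with positive ISH, IHC 3+ with negative ISH), since the example alone does not settle them. Add HER2-negative to the abbreviated criteria in the synopsis so that the two lists agree.

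The cost is a short amendment that changes no endpoint, dose or sample size. No new registration document is needed. The downside is that a few IHC 2+ candidates without an ISH result must have one before registration.
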